[figure not shown]

**DOCUMENT REVISION HISTORY**

Date	Version	Section	Summary of Changes	Author(s)
27March2025	1.0	All	Original Version	[name]
12May2025	2.0	4.4	Removed “willing to provide informed consent” from the inclusion criteria, as it is also an exclusion criteria.	[name]
		4.5	Clarified that patients should be approached by a circle of care member. Clarified the composition and process of the Central Adjudication Committee.	
		9.1	Added text to clarify that participants may use other available social work services or referrals as part of usual care.	

**TRIAL SUMMARY**

Name	Social Worker Presence in Outpatient Fracture Clinics: A Batched Stepped-Wedge Cluster Randomized, Trial
Methodology	Batched Stepped-Wedge Cluster Randomized Trial
Background	To address the unmet needs of orthopaedic trauma patients, we propose integrating a dedicated social worker within the fracture clinic setting.
Primary Objective	The primary objective is to determine if the integration of a dedicated social worker within the fracture clinic setting, compared to usual care, reduces all-cause return to emergency room or urgent care over 6 months.
Secondary Objectives	
The secondary objectives of the definitive trial are to determine if the integration of a dedicated social worker within the fracture clinic setting, compared to usual care:
 
 
1. Reduces negative psychological impact;
 
2. Reduces negative financial impact;
 
3. Increases patient satisfaction with care;
 
4. Reduces opioid use; and
 
5. Reduces missed fracture clinic visits.
 
 
We will assess the economic value of the intervention from the hospital (payer) perspective. Finally, we will explore the lived experiences of orthopaedic trauma patients, social workers, and health care professionals in fracture clinics through structured interviews.

Key Eligibility Criteria	
The key eligibility criteria are:
 
 
1. Adult patient over the age of 18.
 
2. Patient presenting within 12 weeks of injury with an appendicular fracture that required surgical management.
 
3. Willing to comply with the trial protocol.
 

Intervention	Participants enrolled into the treatment group will meet with the social worker, which may include the following interventions: intake and assessment; formulation of goals; treatment planning and intervention; evaluation and conclusion. Participants in the usual care group will receive standard fracture care as determined by their treating surgeon.
Primary and Secondary Outcomes	
The primary outcome is all cause visits to an emergency room or urgent care center within 6 months of enrollment. The secondary outcomes are:
 
 
1. LIMB-Q Psychological Impacts scale.
 
2. LIMB-Q Financial Impacts scale.
 
3. Satisfaction with care question.
 
4. Opioid use at 3 months and 6 months.
 
5. Fracture clinic visits attended and missed.
 
6. Economic analysis (EQ-5D and hospital use).
 
7. Qualitative interviews with participants, social workers, and health care professionals.
 

Sample Size	2000 patients
Significance	This trial has the potential for significant impact on patients including enhanced recovery and health outcomes, prevention of complications and improved long-term recovery. Specifically, this trial has the potential to identify areas in which social workers can have the most significant impact, providing evidence for hospital administrations to offer social work services in fracture clinics.

## 1.0 INTRODUCTION

### 1.1 What is the problem to be addressed?

Each year, approximately 15% of Canadians experience an orthopaedic injury serious enough to affect their ability to engage in everyday activities. These injuries include fractures and dislocations that are typically managed operatively by an orthopaedic trauma surgeon and frequently result in prolonged recovery periods. Despite a comprehensive and well-researched approach to medical aspects of recovery, this patient population seldom receives adequate social support for the non-physical consequences of their injuries.

Following a serious orthopaedic injury, patients may face numerous life changes including negative impacts on relationships, independence, emotional well-being, financial stability, and ability to work or participate fully in daily activities. Patients may also experience new or worsening mental health problems. Studies have found orthopaedic trauma patients to have higher-than-average rates of many types of mental health disorders, including depression and anxiety. A 2017 systematic review found that, post-injury, the weighted pooled prevalence of depression and post-traumatic stress disorder in orthopaedic trauma patients was 33% and 27%, respectively. Post-injury, there is a correlation between symptoms of depression and reduced physical function and magnitude of disability.

As they often necessitate prolonged periods away from work, traumatic orthopaedic injuries significantly affect employment and income. For many, financial repercussions are immediate, leading to income loss even with minor injuries. It is not uncommon for physical impairment from orthopaedic injuries to keep patients from returning to work for 6 months or more, with compounding detrimental effects on relationships, self-worth, and future job prospects. Research on the financial toll of orthopaedic injuries found that fractures were associated with substantial individual and household income loss up to 5 years after injury, and 1 in 5 patients sustained catastrophic income loss in the 2 years after their injury. Navigating the bureaucratic and logistical challenges of securing employment insurance or Workplace Safety and Insurance Board benefits post-injury can be overwhelming, adding to the burden faced by the injured person or their caregivers.

The stress of a serious orthopaedic injury may also lead to or exacerbate substance abuse problems, which may include increased alcohol intake and drug use. In addition, opioids are a ubiquitous part of perioperative pain management following an orthopaedic injury. Despite increasing regulations, more than 80% of orthopaedic trauma patients are prescribed opioids in the post-surgical period. Patients may have low levels of information about safe opioid use, alternative methods of pain management, and what to expect during recovery. When coupled with other post-injury challenges, including mental health issues, job loss, and income reduction, these factors may lead to opioid addiction, potentially resulting in permanent job loss, being without a home, and even death.

The combined stress of physical recovery, financial strain, risk of addiction, changes in relationship dynamics, and the intricacies of obtaining aid or services can be emotionally and mentally taxing for orthopaedic patients and their support networks. Orthopaedic trauma patients urgently need outpatient support for their recovery from injury. The orthopaedic fracture clinic is the only outpatient care that these patients receive. Supplementing medical treatment with a comprehensive support system and strategies to mitigate the non-physical impacts of orthopaedic injury has the potential to significantly reduce the negative impact of these traumatic injuries. To address this urgent social need, we propose the integration of a dedicated social worker within the fracture clinic setting to provide support to patients with serious orthopaedic injuries. A clinical trial is needed to evaluate the efficacy of having a social worker in the fracture clinic before widespread hospital policy changes can be implemented.

## 1.2 Why is a trial needed now?

The functional impact of a serious orthopaedic injury significantly influences patients' ability to work, participate in activities of daily living, engage in exercise and sports, maintain social relationships, and feel like a valued member of their family and society – all areas in which a social worker can have a pivotal impact. Post-pandemic, North America has faced growing mental health, opioid use, and cost of living crises which have left Canadians susceptible to a post-injury cascade of social and financial consequences. In preparation for the proposed trial, we conducted a search of the literature, which identified a trial that evaluated rates of osteoporosis treatment in hip fracture patients. The results of this trial directly led to the addition of an osteoporosis coordinator to assess the bone health of fracture patients in many fracture clinics across Canada. The success of the osteoporosis coordinator model became the basis for our hypothesis that a similar model providing dedicated social worker support in fracture clinics will reduce the negative life impact of orthopaedic injury on patients. Our search did not identify any trials evaluating social worker support in fracture patients.

We conducted a cross-sectional survey of practicing orthopaedic surgeons who treat patients with serious orthopaedic injuries and asked about their perceptions regarding the need for social worker support in their patient population. Orthopaedic surgeons identified that they are 'often' or 'always' seeing patients who are financially strained (84%), experiencing substance abuse (53%), have mental health problems (38%), or are underhoused (35%). In addition, 84% of respondents indicated that at least one social support required by their fracture patients was currently inadequate to a point of crisis.

To ensure that patients' voices are heard, we conducted a cross-sectional study of 200 patients receiving treatment for an orthopaedic injury in the fracture clinic setting. Critically, 94% of patients surveyed indicated that they believe that fracture patients like them would benefit from the support of a social worker. From the patient perspective, patients identified multiple areas of support that a social worker could provide, with over 60% of respondents indicating patients like them could use assistance with benefits/insurance, coordination of care, counselling and emotional support, referrals, post-traumatic stress disorder, patient education, needs assessments, anxiety, inability to pay for care, depression, family support, patient advocacy, advocacy for vulnerable

population, crisis intervention, substance misuse, financial strain, intimate partner violence, and being unhoused or underhoused.

Our review of the literature, coupled with insights from orthopaedic surgeons and patients, has identified a critical gap in patient care in outpatient fracture clinic settings. Despite this need being recognized by many surgeons and patients with whom we have engaged, the current standard of care fails to address these non-physical concerns. Our body of work to date underscores the urgency and importance of bridging this gap: one in which social workers could enhance patient well-being and where they are uniquely poised to contribute to the current landscape of orthopaedic treatment. To address this issue, this trial aims to evaluate the impact of integrating a dedicated social worker into outpatient fracture clinics.

## 2.0 OBJECTIVES

The primary objective of this trial is to determine if the integration of a dedicated social worker within the fracture clinic setting, compared to usual care, reduces all-cause visits to the emergency room or urgent care over 6 months.

The secondary objectives of this trial are to determine if the integration of a dedicated social worker within the fracture clinic setting, compared to usual care:

1. Reduces negative psychological impact;
2. Reduces negative financial impact;
3. Increases patient satisfaction with care;
4. Reduces opioid use; and
5. Reduces missed fracture clinic visits.

We will assess the economic value of the intervention from the hospital (payer) perspective. We will also explore the lived experiences of orthopaedic trauma patients, social workers, and health care professionals in fracture clinics through structured interviews.

## 3.0 TRIAL DESIGN

### 3.1 Description of the Trial Design

[figure not shown]
To efficiently and effectively address the above objectives, we have designed this trial as a batched stepped-wedge cluster randomized trial. The batched stepped-wedge cluster randomized trial is a pragmatic design commonly used in the evaluation of service delivery interventions. In the batched stepped wedge trial, clusters (in this case, surgeon clinics) of patients can be randomized and move through the trial design in ‘batches’ (e.g. a group of four clusters), which allows for flexibility in the timing of initiation of different clusters. The stepped wedge design itself begins with each cluster in the batch being given a date for crossover into the treatment group, in a randomly determined order. All clusters then enter an initial period in which no patients are exposed to the intervention. Subsequently, at regular intervals (“steps”), clusters cross from the control to the intervention under evaluation. This process continues until all clusters have crossed over to the intervention. At the end of the batch period there is a period when the intervention is being

implemented at all clusters. Data collection takes place throughout the batch period, so that all clusters contribute observations under both control and intervention observation periods. We will define a cluster as an individual orthopaedic surgeon fracture clinic.

We will conduct this trial in two to four batches, with four clusters in each batch. The number of batches will depend on the enrollment rates during the previous batches. For each batch, before participant enrollment begins, the Methods Centre will randomize the clusters (i.e. clinics) to determine when they will begin the intervention (i.e. social worker support in the fracture clinic). All clinics in the batch will begin participant enrollment into the non-intervention arm (i.e. usual care with no social worker services). At 10 weeks, one clinic will begin the intervention while the others will continue enrolling in the non-intervention arm as per randomization. At 20 weeks the second clinic will cross over to begin treatment, and at 30 weeks the third clinic will crossover. The fourth clinic will cross over after 40 weeks. All clinics (clusters) will enroll for 12 months.

To ensure feasibility of this design, we will conduct a Vanguard phase that will include two clusters who will enroll for a period of 8 months. As per the above, both clusters will be participant enrollment into the non-intervention arm (i.e. usual care with no social worker services). At 10 weeks, one cluster will begin the intervention while the other cluster will continue enrolling in the non-intervention arm as per randomization. At 20 weeks the second cluster will cross over to begin treatment. Participant enrollment in both clusters will continue for 10 additional weeks. Data from the vanguard phase will be included in the trial, if there are no significant changes to the protocol.

Figure one shows the trial design, which includes the vanguard phase (in purple) and then a batched stepped-wedge design (in green). Batch timelines may also overlap each other, and the timing will depend upon funding and the readiness of different clusters to begin recruitment. The overall sample size for the trial will be approximately 2,000 participants.

## 4.0 METHODOLOGY

### 4.1 Trial Setting

The Surgery Methods Centre in the Department of Surgery at McMaster University will coordinate this trial. The Methods Centre will register this trial on ClinicalTrials.gov prior to initiating enrollment. The Principal Investigator will chair the trial's Steering Committee, which will provide oversight and guidance for the trial. Methods Centre personnel will obtain research ethics board approval for the trial. Research personnel at each selected cluster (the institution affiliated with each cluster) will obtain local Research Ethics Board approval prior to initiating local trial activities. Clusters will be selected at hospitals in the United States and Canada.

### 4.2 Cluster Eligibility and Selection of Clusters

Clusters will be defined by orthopaedic surgeon clinical practices and participating sites may contribute one or more clusters. Clusters will be selected in batches of four. Methods Centre personnel will carefully screen potential clusters for eligibility. Cluster inclusion criteria are: 1) adequate research personnel infrastructure to manage the trial; 2) adequate surgically managed fracture volume to complete enrollment within the timelines; and 3) ability to secure a qualified social worker to perform the trial intervention. The exclusion criteria are: 1) lack of interest in the trial; 2) anticipated challenges with complying with the protocol; 3) conflicting studies that would inhibit patient participation; and 4) budgeting or contract constraints.

The screening process will begin with potential clusters (orthopaedic surgeons' clinics) completing a feasibility questionnaire that includes the cluster eligibility criteria. Clusters that meet the

eligibility criteria at this stage will be invited to participate in a meeting to review local logistics and to confirm interest and eligibility. Study personnel will document reasons for cluster ineligibility.

Of note, clusters (individual orthopaedic surgeons clinic days) within the same batch and across the batches may be at the same or different hospital and/or university.

We will document key demographic information for each cluster.

#### **4.3 Cluster Allocation and Concealment**

The Methods Centre will randomize each batch of clusters prior to the start of patient recruitment to determine when they will begin the intervention. At the time of randomization, Methods Centre personnel will notify each cluster of the timing of their crossover from usual care to the treatment phase of the trial.

#### **4.4 Participant Eligibility Criteria**

The screening population for this trial is patients 18 years of age or older with an injury to the appendicular skeleton which occurred in past 12 weeks and required surgical management who present to a participating fracture clinic.

The inclusion criteria are:

1. Aged 18 or older.
2. Had a fracture of the appendicular skeleton.
3. Fracture required surgical management.
4. Fracture occurred within the past 12 weeks.
5. Willing to comply with the protocol.

The exclusion criteria are:

1. Incarceration.
2. Expected injury survival of less than 6 months.
3. Terminal illness with expected survival of less than 6 months.
4. Currently enrolled in a trial that does not permit co-enrollment.
5. Unable to engage in protocol in the languages available in the local cluster.
6. Prior enrollment in the trial.
7. Declined to provide informed consent.
8. Not approached at (or prior to) the first post-surgery fracture clinic visit (missed participant).
9. Other reason to exclude the patient, as approved by the Methods Centre.

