#### **4.6 Intervention**

Research personnel at each cluster will inform individual participants of their treatment allocation **after** they have provided informed consent. Participants enrolled during the usual care phase at their clinic will attend appointments as usual on a schedule determined by their surgeon and will not have access to social worker support in the fracture clinic.

Participants enrolled during the treatment phase at their clinic will receive social work support (see Table 1) for 6 months from the time of enrollment. They will have an intake appointment with the social worker before or during their initial fracture clinic visit to assess their needs, identify goals that they can address with the support of the social worker, and collaboratively formulate a personalized care plan tailored to their specific circumstances. The social worker will then implement the plan, which may involve educating participants and their support network, coordinating delivery of care and benefits, making referrals to community services, advocating for the participant, and providing emotional support and brief counselling. The social worker will be accessible to participants for 6 months post-enrollment, following up via telephone, telemedicine or in-person to evaluate the effectiveness of the care plan and offer sustained ongoing support. During this time, the social worker will make detailed notes on communication and referrals provided.

Table 1: Social Worker Support

1. Intake and Assessment: The social worker will complete a standardized intake assessment questionnaire that will ask the participant about their social needs. This will include asking about safety, intimate partner violence, addictions, housing and utilities, finances, food insecurity, mental health, transportation, and injury recovery.
2. Formulation of goals: Based on the intake and assessment, the social worker will work with the participant to identify goals the social worker can help the participant achieve. An example of a goal is “plans for childcare during physiotherapy appointments”; “manage my stress and anxiety since the car accident”; “help to stop drinking”; “try to get off pain medications”; or “get a walker while on a fixed income”.

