## 4.7 Outcomes

The primary outcome measure is all cause visits to an emergency room or urgent care centre within six months of enrollment. (See Section 4.7.1).

Secondary outcome measures are:

1. LIMB-Q Psychological Impacts scale (See Section 4.7.2).
2. LIMB-Q Financial Impacts scale (See Section 4.7.2).
3. Satisfaction with care provided (See Section 4.7.3)
4. Opioid use (See Section 4.7.4).
5. Fracture clinic visits attended and missed (See Section 4.7.5)
6. Economic analysis (EQ-5D-5L and hospital use) (See Section 4.7.6)
7. Qualitative interviews with participants, social workers, and health care professionals (See Section 4.7.7).

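### Eligibility dates the approach but not the consent, so a patient approached shortly before a clinic's known crossover can be enrolled on either side of it

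*Protocol*

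**What the plan says.** All places are in the protocol.

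- **Approach (4.4).** Exclusion 8 removes a patient who was "Not approached at (or prior to) the first post-surgery fracture clinic visit (missed participant". Approach may therefore come before that visit, although the screening population is described as patients whose injury "required surgical management who present to a participating fracture clinic".
- **Other time limit (4.4).** "Fracture occurred within the past 12 weeks". The date at which this is judged is not stated.
- **Consent (4.5).** A member of the circle of care makes the approach, research personnel then confirm eligibility, and the consent process follows. No interval is set between these steps.
- **Arm (4.6).** "Participants enrolled during the usual care phase at their clinic" get no social worker support in the clinic. By contrast, "Participants enrolled during the treatment phase at their clinic will receive social work support". Intake for the latter takes place no later than the initial fracture clinic visit.
- **Knowledge of the schedule (4.3, 4.9).** At randomization, before recruitment, "Methods Centre personnel will notify each cluster of the timing of their crossover from usual care to the treatment phase of the trial". Participants, trial personnel and clinicians are not blinded.
- **Steps (3.1).** The four clinics of a batch cross over at weeks 10, 20, 30 and 40 and enrol for 12 months.

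**The concern.** In a stepped wedge trial that recruits patients as it goes, the random element is the order in which clinics cross over. A patient's arm inherits that randomness only if staff cannot choose on which side of the crossover the patient falls. Here the arm depends on the enrolment date, which the protocol appears to treat as the consent date, since it uses the two terms interchangeably. Consent is the one step between approach and treatment that has no date limit, and the people who arrange it know when the social worker starts.

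An understandable motive exists. In the survey reported in section 1.2, 84% of surgeons said that at least one support their fracture patients need was inadequate to the point of crisis. Someone who sees a patient in clear need a week before the social worker arrives could wait with the consent form out of good will. If high-need patients are held over, the usual-care group loses high-risk patients and the treatment group gains them, which shrinks the apparent benefit. If low-need patients are the ones deferred, the shift goes the other way and favours the intervention. The direction is thus not reliably conservative.

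**Working it through.** **Does any rule close the gap?**

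1. Exclusion 8 limits approach, not consent.
2. The 12-week fracture criterion is at most an outer bound. It is longer than the 10-week step, so it does not by itself keep a patient on one side of a crossover.
3. The intake rule in 4.6 implies consent by the initial visit, but only for the treatment phase. It is a treatment procedure, not an exclusion, and has no usual-care counterpart.
4. Section 4.6 has participants told their allocation only after consent. That conceals it from the participant, not from staff who know the schedule.

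None of the four sets a consent deadline in both phases.

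**How large could the effect be?** The protocol gives no figure for this, so what follows is an illustration.

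From the protocol: planned rates of 14.8% and 10% (section 5.0), difference 14.8 − 10 = 4.8 points; usual-care durations of 10, 20, 30 and 40 weeks, total 100 clinic-weeks per batch (3.1).

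Assumed: even enrolment; patients approached in the last w weeks before crossover can be moved; the highest-need quarter of them are all moved; their risk ratio r against the other three quarters is 1.5 to 2; the treatment effect is the same relative effect in everyone (10/14.8); the two groups start equal in size.

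*Movable share of usual-care enrolment:* Σ min(w, T) / Σ T.
- w = 2: 8/100 = 8%, so the moved fraction is m = 0.25 × 0.08 = 0.02.
- w = 5: 20/100 = 20%, so m = 0.25 × 0.20 = 0.05.

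*Usual-care risk of the high-need quarter:* h = r × 14.8 / (0.75 + 0.25r).
- r = 1.5: h = 1.5 × 14.8/1.125 = 19.73%.
- r = 2: h = 2 × 14.8/1.25 = 23.68%.

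*Observed rates:* control = (14.8 − m·h)/(1 − m); treatment = (10 + m·h·10/14.8)/(1 + m).

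| w | r | Control | Treatment | Difference |
|---|---|---|---|---|
| 2 | 1.5 | (14.8 − 0.395)/0.98 = 14.70 | (10 + 0.267)/1.02 = 10.07 | 4.63 |
| 2 | 2 | (14.8 − 0.474)/0.98 = 14.62 | (10 + 0.320)/1.02 = 10.12 | 4.50 |
| 5 | 1.5 | (14.8 − 0.987)/0.95 = 14.54 | (10 + 0.667)/1.05 = 10.16 | 4.38 |
| 5 | 2 | (14.8 − 1.184)/0.95 = 14.33 | (10 + 0.800)/1.05 = 10.29 | 4.05 |

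**Sensitivity to the estimator.** The table compares pooled rates. A stepped-wedge estimator with period effects relies more on comparisons near each crossover and reacts more strongly. Generalised least squares was applied to expected cluster-period rates (47 patients per cluster-period, ICC 0.05, no true effect). Moving half of a high-risk quarter over a 4-week window moves about 1% of all patients. It shifts the estimated risk difference by 0.85 points (risk ratio 2) to 1.4 points (risk ratio 3), which is 18% to 29% of 4.8. Section 6.1 does not mention a period term in the primary model, so this shows sensitivity and is not a forecast.

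**The case against.** The best counter-argument is that the opening is narrow. A patient held over enters the treatment phase, exactly where the intake rule of 4.6 applies. Holding someone past the first clinic visit would depart from that rule. This stands: the clearly open case is a patient approached before the first visit, with the crossover falling between approach and that visit. It does not remove the point, because missing the intake time is not an exclusion and the patient would still be analysed in the treatment arm.

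It is also fair to say that the protocol shows no misuse and that the assumptions above are generous. The protocol does not give the usual gap between approach and first visit, so the 5-week case may be too wide.

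Three stronger readings are tempting, and the documents do not support them.

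- *The whole 10-week step can be steered.* That would need patients held for weeks with their first visit still ahead, or in disregard of the intake rule. Nothing in the protocol suggests holds of that length.
- *The protocol contradicts itself on late consent.* It does not. A late consent would depart from the intake procedure in 4.6, but no two passages conflict.
- *The outcome clock adds a bias.* The primary outcome counts "all cause visits to an emergency room or urgent care centre within six months of enrollment", so early emergency visits count for a patient enrolled on the ward and not for one enrolled at the first visit. Both kinds can occur in both phases. A bias needs the mix to change at crossover, and nothing in the protocol shows that it would.

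**Conclusion.** The point holds in a limited form. The protocol sets no consent deadline, lets the enrolment date decide the arm, and gives unblinded staff the crossover date. Patients approached shortly before a crossover can be consented on either side of it without breaching any eligibility criterion. The intake rule discourages this past the first visit but does not prevent it.

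If the highest-need quarter were all held over at a risk ratio of 1.5 to 2, the loss would be about 0.2 to 0.3 of the 4.8 points for a 2-week window and 0.4 to 0.75 for a 5-week window. A model with period effects could shift more. The window length, the share moved and the risk ratio are all assumptions. A reader might infer that the trial's result will be biased, but the documents establish opportunity only. The change is still worth making before recruitment, because selective timing would be hard to detect or correct afterwards.

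**What to change.** 1. In 4.4, make consent by the end of the first post-surgery fracture clinic visit a condition of eligibility in both phases. This agrees with the intake timing in 4.6.
2. Record the date of approach. The deadline narrows the window but does not close it for patients approached before that visit, and the approach-to-consent interval can then be compared before and after each crossover.
3. Include days from surgery to enrolment as a covariate in the primary model in 6.1. This adjusts for timing; it cannot fully undo selection on unmeasured need.

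The cost is a sentence in 4.4, one date field, one covariate, and the few patients who would have decided after the visit. The sample size calculation does not change.

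Assigning the phase, or starting the outcome clock, at the first clinic visit is not recommended. Appointments follow a schedule set by the surgeon, so that date can also be moved. Intake may precede the visit, so emergency visits after the intervention began could go uncounted. A participant may also miss the visit, and missed visits are themselves an outcome.
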